# Follow-up examination or early withdrawal

All participants will have a follow-up visit by telephone (Visit 8) at 2 weeks  $\pm 2$  days after the last dose of study intervention. Participants who prematurely withdraw from the study should complete Visit 7. Participants who continued treatment to the end of the double-blind treatment period (Week 12) or have completed the study as per Section 7.2 will continue to collect information on the number of seizures they experience using the e-diary until 2 weeks after the last dose of study medication. The procedures to be completed during this visit are listed in the SoA.

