Participants who continued treatment to the end of the double-blind period (Week 12) or have completed the study (as defined above) and have not elected to participate in the OLE will go into the follow-up phase. In the follow-up phase, participants will continue to record only the number of seizures using the e-diary until 2 weeks after the last dose and will have a telephone follow-up visit at 2 weeks ± 2 days after the last dose. The analysis reference start date of the follow-up analysis phase is the day after the reference end date for the double-blind phase. The analysis reference end date of the follow-up analysis phase is the maximum of the telephone follow-up visit date or the e-diary follow-up date.

Open-Label Extension Phase

For participants electing to participate in the OLE, the reference start date of the OLE phase will be either the date of last study drug intake by the participant in the double-blind period for subjects who continue into the OLE without an interruption of ≤4 weeks from the double-blind period, or the date of the OLE baseline visit when there is an interruption of >4 weeks (i.e. the last visit of the double-blind period was more than 4 weeks ago). Participants participating in the OLE without an interruption of ≤4 weeks from the double-blind period will not have the follow-up visit (Visit 8), and those with an interruption of >4 weeks will complete the follow-up visit. The analysis reference start date for the OLE phase is the date of the last dose taken in the double-blind phase. The analysis reference end date of the OLE phase is either the date when the last dose of study drug is taken in the OLE phase (Visit OLE11), the date OLE is stopped by the sponsor or the date of early withdrawal from the OLE phase. The open-label efficacy data will be summarized by the double-blind treatment group in the form of an intervention sequence (PBO/JNJ and JNJ/JNJ).

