5.5.2.2. Analysis Methods

To evaluate the CCI , descriptive statistics (N, mean, standard deviation, median, minimum, and maximum) for actual values for the weekly seizure count during each study period (baseline, double-blind and follow-up) will be provided by treatment group (JNJ-813) pooled over CCI , and also treatment group by CCI

for all observable focal-onset seizures. Mean (\pm SE) plot for the weekly seizure count will be provided for each week by treatment group and by stratum.

Furthermore, the following additional safety findings will be reported:

- for each cohort the number and percentage of participants with cluster seizures will be summarized by treatment group (JNJ-813) pooled over treatment group by GCI within each study period (baseline, double-blind and follow-up).
- for each cohort the number and percentage of participants in the follow-up period with focal to bilateral tonic-clonic seizures who had none reported in the baseline or double-blind period will be summarized by treatment group (JNJ-813) pooled over and also treatment group by
- for each cohort the number and percentage of participants in the follow-up period with a seizure rate that is more than twice that of the baseline monthly seizure count will be summarized by treatment group (JNJ-813) pooled over treatment group by The follow-up monthly seizure count is defined as the total number of observable focal onset seizures occurring during the follow-up period, multiplied by 28/X_{FU}, where X_{FU} is the number of days comprising the follow-up period.

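### When the follow-up call falls after the diary has stopped, the follow-up seizure rate is divided by days without seizure recording, so the more-than-twice-baseline safety percentage can be under-counted

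*SAP*

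**What the plan says.** SAP 5.1 (Follow-up Phase) sets the start: "The analysis reference start date of the follow-up analysis phase is the day after the reference end date for the double-blind phase". The double-blind phase ends on the Visit 7 date. It sets the end as follows: "The analysis reference end date of the follow-up analysis phase is the maximum of the telephone follow-up visit date or the e-diary follow-up date".

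The same paragraph describes data collection: "participants will continue to record only the number of seizures using the e-diary until 2 weeks after the last dose". The call is set at 2 weeks with a window of 2 days either side. Protocol 4.1 (Follow-up examination or early withdrawal) gives the same timing: "All participants will have a follow-up visit by telephone (Visit 8) at 2 weeks", with the same window, and it also stops the diary 2 weeks after the last dose.

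SAP 5.5.2.2 defines the follow-up monthly count as the observable focal onset seizures in follow-up, "multiplied by 28/X_{FU}, where X_{FU} is the number of days comprising the follow-up period". Among its additional safety findings it lists the number and percentage of participants "with a seizure rate that is more than twice that of the baseline monthly seizure count".

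SAP Table 2 runs the follow-up row for e-diary seizure counts from the end of the double-blind phase to the end of follow-up, with a target of 14 days after the double-blind phase ends.

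**The concern.** Taking the later of two dates means a phone call can set the denominator of a rate whose numerator comes only from the diary. If the call is late, the days between diary end and call enter X_FU with no seizures recorded on them. If the call is early, nothing compensates, because the maximum then returns the diary date. The error therefore runs one way.

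That direction matters. Protocol 4.2 (Duration of study periods) says the dose is not tapered and that follow-up is used to examine seizure counts after treatment stops. An over-long denominator pulls the summary away from showing a rise. Whether a participant is flagged could depend on which permitted day the site telephones.

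The comparison is also uneven. SAP 5.1 ties the baseline phase to the diary at both ends: it opens when the e-diary is initiated and closes when the baseline is entered as complete in the diary dashboard. Only the follow-up denominator can be extended by a phone date.

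**Working it through.** **Inputs**
- Follow-up starts the day after Visit 7; its end date is the later of the call and the e-diary follow-up date (SAP 5.1).
- The diary is planned to day 14 after the last dose; the call falls on days 12 to 16 (SAP 5.1).
- Dosing runs to Day 85, or to the day of Visit 7 if that is earlier (Protocol 6.1).
- A participant is flagged if count × 28/X_FU exceeds 2B, where B is the baseline monthly count (SAP 5.5.2.2).

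**The plan's own timing.** 85 + 14 = Day 99, with a window of Day 97 to Day 101. This agrees with Visit 8 in the protocol Schedule of Activities and with the Table 2 target of 14 days.

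**Last dose on the Visit 7 day, diary stopping on day 14.** X_FU = max(call day, 14). Rate error = 14/X_FU - 1. Ratio needed for a flag = 2 × X_FU/14.

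| Call day | X_FU | Rate error | Flag only above |
|---|---|---|---|
| 12, 13, 14 | 14 | 0 | 2.00 × baseline |
| 15 | 15 | 14/15 - 1 = -6.7% | 2.14 × baseline |
| 16 | 16 | 14/16 - 1 = -12.5% | 2.29 × baseline |

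**Example.** B = 8, so the limit is 16. Nine seizures in 14 diary days give 9 × 28/14 = 18, flagged. With X_FU = 16 they give 9 × 28/16 = 15.75, not flagged.

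**Whole counts.** The smallest flagging count is floor(2 × B × X_FU/28) + 1. From X_FU = 14 to 16 it does not change at B = 3, 4, 5 or 6. It rises from 8 to 9 at B = 7, 11 to 12 at B = 10, 21 to 23 at B = 20 and 31 to 35 at B = 30. A 56-day baseline also allows half values. At B = 3.5 it rises from floor(3.5) + 1 = 4 to floor(4.0) + 1 = 5, so low baselines are not all exempt.

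**Last dose before Visit 7.** With a gap of g days, 14 - g diary days are divided by 16 - g for a day-16 call. A gap of 2 days (last dose on Day 85, Visit 7 on Day 87, inside its window) gives 12/14 - 1 = -14%. An assumed gap of 7 days gives 7/9 - 1 = -22%.

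**Call outside the window.** An assumed call on day 21 gives 14/21 - 1 = -33%.

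**Effect on flagging (simulated).** Assumptions: individual rates lognormal, median 10 per 28 days, SD of the log 0.9; participants kept if both 4-week baseline counts are 3 to 100; a 14-day diary; counts Poisson, or gamma-Poisson with shape 5 per period.

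| True rise | Model | X_FU = 14 | X_FU = 16 for all | Loss in points, all calls day 16 | Loss in points, calls even over days 12-16 |
|---|---|---|---|---|---|
| 2 × | Poisson | 44.5% | 30.4% | 14.1 | 4.0 |
| 2 × | Overdispersed | 42.7% | 35.6% | 7.1 | 1.9 |
| 2.5 × | Poisson | 71.0% | 57.9% | 13.1 | 3.6 |
| 2.5 × | Overdispersed | 56.2% | 49.1% | 7.1 | 2.0 |

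The even spread of calls is an assumption. The columns with every call on day 16 are the in-window worst case when the last dose falls on the Visit 7 day.

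**The case against.** The best reply is that a hard diary stop on day 14 is not certain. The Schedule of Activities (Protocol 1.2) marks e-diary seizure counts in the Visit 8 column, which carries a window of 2 days either side. Table 2 describes continuous collection to the end of follow-up. If participants keep entering seizures until the call, numerator and denominator cover the same days and there is no error. The e-diary follow-up date is not defined, and the documents never state that the follow-up period in SAP 5.5.2.2 is the follow-up analysis phase of SAP 5.1. Both links have to be read in.

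This stands in part. It makes the effect conditional. It does not remove it, because the text in both documents stops the diary 2 weeks after the last dose, SAP 5.1 is the only definition of the follow-up end date, and nothing restricts X_FU to diary days. SAP 5.3.1 also treats days without diary data as seizure-free. That rule is written for the primary endpoint and its use in follow-up is inferred, but nothing in SAP 5.5.2.2 removes such days from X_FU.

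A reader might infer that a rise after withdrawal would be hidden. The documents do not support that. The percentage is one descriptive figure in the exploratory section, with no test and no decision rule. The same section reports weekly seizure counts with week-by-week plots, cluster seizures, and focal to bilateral tonic-clonic seizures new in follow-up, none of them defined through X_FU. The date rule is the same in both arms, and follow-up covers only participants who do not go straight into the open-label extension.

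**Conclusion.** Wrong as written; minor. Whenever the phone date is later than the end of diary recording, X_FU includes days on which no seizures were being recorded. The follow-up rate is then too low, and the more-than-twice-baseline percentage can be under-counted but not over-counted from this cause. Within the window, and with the last dose on the Visit 7 day, the rate error is at most 12.5%. It changes the flag only for participants whose observed ratio lies above 2.00 and no higher than 2.14 (day 15) or 2.29 (day 16).

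A reader might infer that the percentage is under-counted throughout, or by about 14 points. Neither follows. Calls on days 12 to 14 cause no error, a diary that stays active until the call causes none, and the 14-point figure needs every call to fall on day 16.

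The conclusion rests on the diary stopping as the text plans, and on the follow-up period in SAP 5.5.2.2 being the phase defined in SAP 5.1. The primary endpoint and the double-blind secondary endpoints do not use X_FU and are unaffected.

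**What to change.** In SAP 5.1, define the e-diary follow-up date as the last day the follow-up diary was active. It should not be the date of the last seizure entry, which would drop seizure-free days at the end and push the rate up.

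In SAP 5.5.2.2 and in the follow-up row of Table 2, set X_FU to the days from the day after Visit 7 to that date, and count seizures over exactly those days. Do not impose a fixed 14-day cap: if a diary was in fact kept to day 15 or 16, a cap would discard seizures that were recorded after withdrawal. Keep the maximum of the two dates only as the phase end for non-seizure data.

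The cost is a sentence or two in the SAP and one derived date, with no new data collection. Participants with a short diary period will have a somewhat noisier rate.

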## 10.4. Design of the OLE period

#### 10.4.1. Overall Design

# Overview of the open-label period:

For each participant, the open-label period will start immediately after the last study drug intake by the participant in the double-blind period. Participants participating in this open-label period will not have the follow-up visit (Visit 8) as mentioned in the SoA in Section 1.2.

The participants will continue to take the same concomitant AEDs as used during the double-blind period of the study. During the open-label extension period, dosages of the concomitant AEDs may be changed when needed. A concomitant AED may be added or stopped during the open-label extension period. However, if JNJ-40411813 is no longer of benefit when used in the new combination of AEDs, the participant should stop participating in the study.

Participants will continue to enter their seizures and adverse events in an (e-)diary. After 1 and 2 months and thereafter every 3 months, the subject will visit the study center for review of seizures and safety assessments including vital signs and safety laboratory.

The study assessments will be completed as described in the SoA in Section 10.10.

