## 10.8.2. Study procedures

#### 10.8.2.1. Baseline visit

For participants who continue with an interruption of  $\leq 4$  weeks from the double-blind period:

- The study will start immediately after the last study drug intake by the participant in the double-blind period.
- Participants will have to complete the last visit in the double-blind treatment period but will
  not have the follow-up visit.

• The last visit in the double-blind period will be considered the baseline visit of open-label period. Assessments required for the last visit in the double-blind period and for the baseline of the open-label-period, do not have to be completed twice.

For participants who start the open-label period with an interruption of >4 weeks after completing the double-blind period:

- Complete the follow-up visit when the open-label period has not been started yet.
- The baseline visit for the open-label period should be a new visit when visit 7 of double-blind study period was more than 4 weeks ago.

The baseline examination will consist of the following:

- Review inclusion/exclusion criteria for the open-label period
- Physical and neurological examination (including body weight)
- Supine vital signs (systolic and diastolic blood pressure, heart rate and oral or tympanic temperature)
- Clinical safety laboratory assessments under fasted conditions (at least 4 hours), when feasible (including hematology, serum chemistry and urinalysis)
- Urine pregnancy test for WOCBP
- The C-SSRS (since last visit) is completed by the investigator or qualified delegate.
- Review of concomitant medication including AEDs
- Record AEs
- Dispense study medication

The participant and/or caregiver will be provided access to an (electronic) diary to record seizures. The (e-)diary will be an app downloaded on the smartphone owned by the participant.

Participants must be compliant with the recording of information in the diary throughout the study. Seizures that will be entered throughout the study include focal aware seizures with and without motor signs, focal impaired awareness seizures and focal to bilateral tonic-clonic seizures. Myoclonic, or other generalized seizures will not be entered.

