5.2. Participant Dispositions

The number of participants in the following disposition categories will be summarized throughout the study by intervention group and overall:

- Participants randomized
- Participants who received study intervention during each phase (double-blind and open-label)
- Participants who completed the study during each phase (double-blind and open-label)
- Participants who discontinued study intervention during each phase (double-blind and openlabel)
- Reasons for discontinuation of study intervention during each phase (double-blind and openlabel)

a) Visits occur every 3 months after visit OLE4. To note, the "i" term is the iterator for the 3 monthly visits that occur after OLE4 e.g., i=1 for OLE5

b) Visit windows are as follows: +/- 5 days for OLE2, OLE3 and OLE4 and +/- 7 days for OLE5 and beyond (always to be calculated from OLE1); duration of 1 month is default 31 days until OLE4', duration of 3 months is default 90 days from OLE5 onwards

- Participants who terminated study prematurely during each phase
- Reasons for termination of study prematurely during each phase

Listings of participants will be provided for the following categories:

- Participants who discontinued double-blind study intervention
- Participants who discontinued open-label study intervention
- Participants who terminated study prematurely
- Participants who were randomized yet did not receive study intervention

The above summaries and listings will be provided for the randomized analysis set.

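### For open-label entry after a gap of more than 4 weeks, SAP 5.1 gives two OLE start dates, and one of them puts off-drug days into the OLE seizure rate

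*SAP*

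**What the plan says.** SAP 5.1, Open-Label Extension Phase, sets the reference start date by length of gap. For continuation within 4 weeks it is the last double-blind drug intake; otherwise it is "the date of the OLE baseline visit when there is an interruption of >4 weeks". The same paragraph then adds, with no condition on the gap: "The analysis reference start date for the OLE phase is the date of the last dose taken in the double-blind phase". The introduction to SAP 5.1 says that each phase has its own analysis reference start date, so one date is intended.

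Long gaps are planned for. Protocol 10.4.2 admits participants who finished the double-blind period before the OLE was available to them. Protocol 10.8.2.1 has separate procedures for them: "The baseline visit for the open-label period should be a new visit when visit 7 of double-blind study period was more than 4 weeks ago". For gaps of up to 4 weeks the same section says: "The last visit in the double-blind period will be considered the baseline visit of open-label period".

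SAP 5.5.4 defines the OLE monthly seizure count as all observable focal onset seizures in the OLE period times 28/X_OLE, where X_OLE is the number of days in the OLE. It excludes no gap days. In SAP Table 2 the OLE seizure row runs from the end of the double-blind phase with a target of 730 days after it, yet footnote b to the OLE rows says the visit windows are "always to be calculated from OLE1".

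Follow-up recording is planned only "using the e-diary until 2 weeks after the last dose". SAP 5.1 also says that "those with an interruption of >4 weeks will complete the follow-up visit".

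**The concern.** For a gap of more than 4 weeks, two programmers who each follow a sentence of SAP 5.1 would give the same participant different OLE denominators, and possibly different responder status. The last-dose date counts days on which the participant took no study drug as open-label time.

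The direction of the error depends on the diary. Gap days with no entries that are taken as seizure-free inflate the reduction. Gap days with recorded off-drug seizures dilute a real one. Long-term efficacy is part of the OLE's primary objective (Protocol 10.3), so the rate should describe time on drug.

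Correcting SAP 5.1 alone would not be enough, because the Table 2 seizure row would still start at the end of the double-blind phase.

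**Working it through.** The plan states no figure to reproduce here, so the check compares the 5.5.4 rate under the two start dates.

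**Inputs**
- g = gap days from last double-blind dose to OLE baseline visit. Assumed: 29 (the shortest gap over 4 weeks) and 90.
- L = open-label days. Assumed: 84, 365 and 730. The last is the Table 2 target length.
- r = gap days on which seizures are recorded, at the baseline rate. Either 14 (the planned follow-up diary) or g (whole gap recorded).
- Other gap days count as seizure-free. SAP 5.3.1 states this rule for missing diary days in the primary endpoint; carrying it to the OLE is an assumption.
- d = true reduction on open-label days. The off-drug rate is assumed equal to baseline.
- Open-label dosing is taken to begin on the day of the OLE baseline visit.

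**Formulas**
- OLE-baseline start: X_OLE = L, and the apparent reduction is d.
- Last-dose start: X_OLE = g + L, and the apparent reduction is 1 − (r + L(1 − d))/(g + L).
- Bias = apparent − true = (g(1 − d) − r)/(g + L). It is positive if r < g(1 − d) and negative if r > g(1 − d).
- True reduction that reads as 50%: d = 1 − (0.5(g + L) − r)/L.

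**Worked case, g = 90, L = 365**
- No true effect, r = 14: 1 − (14 + 365)/455 = 76/455 = 16.7%.
- Reads as a 50% responder, r = 14: 1 − (227.5 − 14)/365 = 41.5%.
- True 50%, whole gap recorded: 1 − (90 + 182.5)/455 = 182.5/455 = 40.1%, so the responder is lost.

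| g / L | Off-drug share g/(g + L) | No true effect, r = 14 | True value that reads 50%, r = 14 | True 50%, r = g |
|---|---|---|---|---|
| 29 / 84 | 25.7% | 13.3% | 49.4% | 37.2% |
| 90 / 365 | 19.8% | 16.7% | 41.5% | 40.1% |
| 90 / 730 | 11.0% | 9.3% | 45.8% | 44.5% |
| 29 / 730 | 3.8% | 2.0% | 49.9% | 48.1% |

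Under the OLE-baseline start the last three columns are 0%, 50% and 50% in every row.

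**Gaps of up to 4 weeks.** Both SAP sentences give the last double-blind dose, if the SAP's phrase about being without an interruption of ≤4 weeks is read as with one, as Protocol 10.8.2.1 has it. There is no contradiction. Gap days still enter the rate, but 28 days are 28/758 = 3.7% of a two-year window. If the whole gap is recorded at the baseline rate, a true 30% then reads 0.30 × 730/758 = 28.9%.

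**The case against.** The unconditional sentence has a source. Protocol 10.4.1 says that for each participant "the open-label period will start immediately after the last study drug intake by the participant in the double-blind period". But Protocol 10.8.2.1 gives that immediate start only for interruptions of up to 4 weeks and requires a new baseline visit after longer ones. Protocol 10.8.3.1 calculates the seizure rate between visits, so with a new OLE baseline visit the protocol's own rate already leaves the gap out. The conditional SAP sentence is the one that fits.

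It is also fair that the effect is illustrative. The larger figures need a long gap or a short OLE stay, the zero-seizure rule is borrowed from the primary endpoint, and no direction is established. Such gaps should arise mainly where the OLE was not yet open, and Protocol 10.4.2 asks for entry as soon as it is. All of this limits the size of the problem; none of it removes the contradiction.

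A reader might go further and infer that adverse events become treatment-emergent in both phases, by carrying the last-dose date into SAP 5.6.2. The documents do not support that. The open-label rules there separate entry fewer than 6 days after the last double-blind dose from entry at 6 days or later. If the phase began on that dose, the second group would be empty. The Pre-open label rule also refers to open-label dosing and says that events in the gap are emergent in neither phase. The term needs defining, but the overlap is not what the section describes.

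A reader might likewise infer that the follow-up adverse event rule, which states no upper limit, takes in open-label events, or that follow-up diary days are analysed twice. SAP 5.1 defines the follow-up phase as participants who have not elected the OLE and gives it an end date. SAP 5.5.2.1 limits its analysis of the period after the last dose to participants who decide not to enter the open-label phase. Pre-open label and follow-up events are both non-emergent, so carrying both labels would change no treatment-emergent table.

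**Conclusion.** The concern holds for participants with a gap of more than 4 weeks. SAP 5.1 contradicts itself for them, and the unconditional sentence together with the Table 2 seizure row puts off-drug days into X_OLE. On the assumed lengths, a participant with no true effect shows an apparent reduction of between 2.0% (29-day gap, 730 open-label days) and 16.7% (90-day gap, 365 days). With the whole gap recorded at the baseline rate, a true 50% reads 40.1% in the second case. These results rest on assumed gap and OLE lengths, an off-drug rate equal to baseline, and the treatment of unrecorded days.

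The reach is limited. The documents do not say how many participants have such a gap. OLE efficacy is descriptive, with no hypothesis test (Protocol 10.3 and 10.9.2). The double-blind primary analysis does not use this date, and neither do OLE retention (Protocol 10.8.3.2) or exposure duration (SAP 5.6.1).

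A reader might also infer that the start date for gaps of up to 4 weeks is wrong. It is not in conflict: both SAP sentences agree with each other and with Protocol 10.4.1 and 10.8.2.1. The effect there is small over two years, though larger for someone who leaves the OLE early. No change to that date is needed for the seizure rate.

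**What to change.** - In SAP 5.1, delete the unconditional sentence or limit it to gaps of up to 4 weeks. The OLE baseline visit is then the start for gaps over 4 weeks, both there and in X_OLE in SAP 5.5.4.
- Start the Table 2 OLE seizure row at that same date.
- Correct the phrase about being without an interruption of ≤4 weeks so that it matches Protocol 10.8.2.1.
- As a clarification in SAP 5.6.2, state that the open-label phase start date means the first open-label dose, and that the follow-up adverse event rule applies to participants who do not enter the OLE.

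The cost is a small SAP rewording. OLE reductions may look less favourable for participants whose gap was not recorded, because empty off-drug days would no longer lower their rate.
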